6.4. Subset Analyses

The main analysis of primary efficacy endpoint and key secondary efficacy endpoints will be repeated by subgroups defined through geographical regions, age groups (ages 2–11 years, ages 12–17 years, and ages 18 years and older), and baseline ISGA score (ISGA score 2, ISGA score 3). Subset analyses of these endpoints aim to evaluate the consistency of treatment effect across various subsets. P-values will not be reported here.

Summary of TEAEs and participant discontinuations due to AE will be reported by subgroups defined through geographical regions.

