1.4. Rationale

1.4.1. Study and Dose Rationale

In this China and Japan study, a similar study design to the two global pivotal studies (AN2728-AD-301 and AN2728-AD-302) will be used to investigate the efficacy and safety of Crisaborole Ointment, 2% twice daily (BID) in Chinese and Japanese pediatric and adult subjects (ages 2 years and older) with mild to moderate AD, to support the registration of Crisaborole in China and Japan.

Dose selection for the global pivotal clinical studies was based on safety and efficacy results from Phase 2 studies, and the dose selected was later confirmed to be safe and effective for commercialization by the results of the Phase 3 studies.

Phase 2 Study AN2728-AD-204 compared two concentrations of crisaborole (2% and 0.5%) applied QD or BID in adolescents with mild to moderate AD. The largest dose-related response and the greatest improvement in all 5 component signs and symptoms of AD occurred in the crisaborole 2% BID group, with a notable reduction from baseline in the pruritus score.

The 2% dosage strength of the crisaborole ointment formulation administered BID was selected for study in Phase 3 as the highest well-tolerated dose to maximize the potential for efficacy with minimal safety risk. Results from the Phase 3 trials in which subjects aged 2 years and older with mild to moderate AD were dosed BID for 28 days with Crisaborole

Ointment, 2% confirm the safety and efficacy of this formulation strength and dosing regimen in subjects with mild to moderate AD (AN2728-AD-301, AN2728-AD-302).

Long-term (up to 12 months) intermittent use in this patient population was shown to be safe in a 48-week long-term safety study (AN2728-AD-303).

The safety of the 2% dosage strength was confirmed in additional studies, including maximal use systemic exposure (MUSE) studies (pediatric subjects with AD and adult subjects with psoriasis) and with supra-therapeutic dosing in a TQT study (healthy adult subjects). In the pooled Phase 3 registration studies, higher rates of success in ISGA at Day 29 were observed in the crisaborole group than in the vehicle group for the subgroups of sex, age, race, and ethnicity. The proportion of Asian subjects is around 5%, similar trend was observed in the Asian subgroup of the pooled global pivotal studies, with a success in ISGA of 17.3% in the crisaborole group and 11.1% in the vehicle group. The safety profile of crisaborole was not affected by age, sex, ethnicity, or race.

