9.1. Sample Size Determination

The total sample size of 384 subjects in this study with a 2:1 randomization ratio (256:128) will provide approximately 90% power to detect a 12% difference of percent change from baseline in EASI total score at Day 29 between crisaborole arm and vehicle arm at the 0.05 (2-sided) significance level, CCI

Comparative EASI data relative to vehicle was not collected in previous crisaborole studies. The 12% treatment effect in EASI percent improvement was converted from the ISGA response in the Phase 3 studies using a linear regression equation that evaluated the relationship between ISGA response rate and EASI percent improvement from historical trial

data of other topical products (data on file). From the crisaborole Phase 3 pooled data, the ISGA response rate is 32.1 % for crisaborole and 21.8% for vehicle. The converted EASI percent improvement is 38.9% and 26.8% respectively. The difference of EASI percent improvement between crisaborole and vehicle is approximately 12%.

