1. VERSION HISTORY

Table 1. Summary of Changes

Version/ Date	Associated Protocol Amendment	Rationale	Specific Changes
1 20 Oct 2017	Original 17 Oct 2017	N/A	N/A
2 13 Apr 2020	Protocol Amendment 1 15 Nov 2019	Issuance of a protocol amendment, template change, TLF bold moves	
Update endpoints to align with global clinical development program, including:
 
 • Update the primary and key secondary estimands. • Change primary endpoint from Investigator’s Static Global Assessment (ISGA) to Eczema Area and Severity Index (EASI). • Addition of ISGA as a key secondary endpoint. • Update the analysis for Patient Reported Outcomes (PROs). • Update the analysis for Dermatology Life Quality Index (DLQI), Children’s Dermatology Life Quality Index (CDLQI), Infant’s Dermatitis Quality of Life Index (IDQOL), Dermatitis Family Impact Questionnaire (DFI), Patient Oriented Eczema Measure (POEM), Patient Global Impression of Change (PGIC)/ Observer Reported Global Impression of Change (OGIC). 
[REDACTED]

3 18 Sep 2021	Protocol Amendment 3 18 Dec 2020	To align with the current protocol, specify PPAS criteria, provide further clarification on	
 • Updated Section 2 to align with the current protocol. • Updated the detailed list of PPAS criteria.

Table 1. Summary of Changes

Version/ Date	Associated Protocol Amendment	Rationale	Specific Changes
		analysis and reporting details, add additional analyses to address COVID-19 pandemic impacts.	
 • Added detailed descriptive summary statistics for binary and continuous variables. • Deleted supportive analysis for Section 6.1.1 and Section 6.2.3. • Missing data handlings in Section 6.2.4, Section 6.2.5 and Section 6.2.8 are updated to align with the analysis of primary and key secondary estimands. • Updated the analysis set in Section 6.2.2, Section 6.2.4, Section 6.3.1, Section 6.3.2 and Section 6.3.3 to exclude participants who do not have the chance to achieve the event. • Added additional analyses to address COVID-19 pandemic impacts in Section 6.7. • Added by country safety summaries in Section 6.4.

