6.1.1.1. Main Analysis

- Estimand strategy: Hypothetical.
- Analysis set: FAS.
- Analysis methodology: percent change from baseline in EASI total score at Day 29, will be analyzed using MMRM that includes treatment group, visit, and treatment group-by-visit interaction as factors and baseline value as a covariate. Within-subject variability will be accounted for using a random effect with the first-order autoregressive (AR(1)) covariance matrix.
- Intercurrent events and missing data: data after treatment discontinuation prior to Day 29 will not be considered. Missing values will not be explicitly imputed and will be assumed to be MAR.
- Reporting results:
 - Tables: The sample size, least-squares (LS) mean of percent change from baseline and 95% CI for each treatment, LS mean of difference and the corresponding 95% CI, and p-value will be presented at Day 29.

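### SAP 6.4 sets out to evaluate consistency across subgroups but plans no estimate of how the effect differs between them

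*SAP*

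**What the plan says.** SAP 6.4 gives the method in one sentence: "The main analysis of primary efficacy endpoint and key secondary efficacy endpoints will be repeated by subgroups defined through geographical regions, age groups" (2–11, 12–17, 18 and older) and baseline ISGA score (2 or 3). The purpose follows: "Subset analyses of these endpoints aim to evaluate the consistency of treatment effect across various subsets. P-values will not be reported here".

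The analysis being repeated is, for EASI, the model in SAP 6.1.1.1, which "will be analyzed using MMRM that includes treatment group, visit, and treatment group-by-visit interaction as factors and baseline value as a covariate". It has no subgroup term. Its planned output is "LS mean of difference and the corresponding 95% CI, and p-value will be presented at Day 29". For subsets only the p-value is withdrawn, so I read the plan as giving a difference and a 95% CI per subgroup. By the same logic the ISGA endpoints (SAP 6.2.1.1 and 6.2.2.1) give a risk difference and a 95% CI per subgroup.

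The general methods (SAP 5.2) and the analysis list (SAP Appendix 1) add no treatment-by-subgroup term, no contrast between subgroups and no criterion for calling effects consistent. Section 6.4 is not redacted.

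The regions are not named in 6.4. The study runs only in China and Japan, and the SAP version history describes the new 6.4 safety tables this way: "Added by country safety summaries in Section 6.4". Region therefore most plausibly means country.

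**The concern.** Whether an effect is consistent across subgroups is a question about the difference between subgroup effects. The plan produces the separate effects and leaves that difference to the reader. With no contrast shown and no reading stated, a natural shortcut is to see which intervals exclude zero. That mixes up the size of the effect with the size of the subgroup: a smaller subgroup has a wider interval and will often include zero even when its true effect equals that of the larger one.

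Interpretation of the subgroup tables is at stake, not the primary conclusion. The protocol's rationale is "to support the registration of Crisaborole in China and Japan", so a table with one country's interval clear of zero and the other's not would draw attention. If no between-country estimate has been specified in advance, any such estimate made in reply would be post hoc.

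**Working it through.** **Inputs**
- Protocol 9.1: 384 subjects, 256:128, about 90% power for a 12-point difference, two-sided 0.05.
- SD of percent change in EASI: not visible (text redacted), so back-solved.
- Country split and baseline ISGA split: not given. I assume 50:50, 25:75 and 10:90.
- 2:1 allocation is assumed within each subgroup, with no dropout and the same true effect of 12 points everywhere.

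**The plan's own figure.** The 90% power cannot be reproduced independently without the SD. The implied SD is

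12 / [(1.960 + 1.282) × √(1/256 + 1/128)] = 12 / (3.242 × 0.10825) ≈ 34.2.

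Putting it back returns 90.0% by construction. SDs of 33, 34 and 35 would give 91.9%, 90.3% and 88.6%.

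**Separate intervals read against zero.** For one subgroup, SE = 34.2 × √(1/n₁ + 1/n₂), and the interval excludes zero with probability Φ(12/SE − 1.96).

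- 50:50 (128:64 in each): SE = 34.2 × 0.1531 = 5.24; Φ(2.29 − 1.96) = 63%. Exactly one of two: 2 × 0.63 × 0.37 = 47%.
- 25:75, smaller (64:32): SE = 34.2 × 0.2165 = 7.40; Φ(1.62 − 1.96) = 37%. Larger (192:96): SE = 34.2 × 0.125 = 4.28; Φ(2.81 − 1.96) = 80%. Exactly one: 0.37 × 0.20 + 0.63 × 0.80 = 58%.

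**Between-subgroup difference.** The subgroups are disjoint, so SE = √(SE₁² + SE₂²) and the half-width is 1.96 × SE.

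| Split | P(interval excludes 0), smaller / larger | Exactly one excludes 0 | SE of difference | 95% half-width |
|---|---|---|---|---|
| 50:50 | 63% / 63% | 47% | 7.40 | ±14.5 |
| 25:75 | 37% / 80% | 58% | 8.55 | ±16.8 |
| 10:90 | 17.5% / 87% | 74% | 12.34 | ±24.2 |

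Rounding the SD to 34.1 gives ±16.7 at 25:75. The probabilities depend only on the stated 90% power: a subgroup with share f has an expected z of 3.24 × √f. If the true SD were anywhere from 30 to 38, the exactly-one figure would be 38–50% at 50:50 and 54–58% at 25:75.

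**Three age groups.** About half the sample is under 12. With the rest split between 25:25 and 10:40 of the total (assumed), simulation gives some but not all intervals excluding zero in 77–80% of trials at SD 34.2.

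**Other readings of inconsistency, same true effects.** One estimate is less than half the other in 31% (50:50), 36% (25:75) or 50% (10:90). A reversed sign in one of two subgroups occurs in 2%, 5.5% or 15%, and in any age group in 11–18%.

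**What the contrast can do.** With identical effects, its 95% CI excludes zero 5% of the time per factor. With a true between-subgroup difference of 12 points, it excludes zero with probability Φ(12/7.40 − 1.96) = 37% at 50:50 and Φ(12/8.55 − 1.96) = 29% at 25:75.

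**The case against.** The strongest reply is that the SAP never tells anyone to read subgroup intervals against zero. It withholds p-values in 6.4, and SAP 5.1 decides superiority on the overall comparisons only. That stands. The 47–58% is conditional on one reading; if only a sign reversal counted as inconsistency, the figure would be 2–18% over the splits examined, all age groups included. A reader might infer that identical effects will often look inconsistent whatever the reading. The documents do not support that. They name no reading, and this silence is part of the gap.

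Second, because the subgroups are disjoint, a reader can approximate the difference and its SE from the two reported intervals. This also stands. The addition is mainly one of presentation and advance specification.

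Third, the contrast is weak. At 25:75 its half-width exceeds the whole assumed effect, and a real 12-point difference would be detected only 29% of the time. It would be tempting to state that consistency is judged on this difference. Without a margin, such a rule would usually pass real inconsistency, so I do not propose it.

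Fourth, separate fits allow the variance, correlation and baseline slope to differ by subgroup; a single model with subgroup terms usually holds them common. Re-estimating them within subgroups is a legitimate preference and not a fault.

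**Conclusion.** The gap is real but modest. SAP 6.4 asks whether the effect is consistent and plans no quantity that estimates the difference. If separate intervals are read against zero, equal true effects of 12 points would give a split result in about 47% (50:50) to 58% (25:75) of trials for a two-level factor. This rests on an SD back-solved from the stated power, assumed splits, 2:1 allocation within subgroups and no dropout.

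A reader might also infer that the country comparison is the planned evidence that the pooled result applies in both countries. The documents do not say so. Protocol 1.4.1 says the study supports registration in both, and SAP 6.4 lists region as one of three factors with no priority.

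The primary result, the alpha level and the gatekeeping order are unaffected. This is a worthwhile, cheap improvement and not a defect in the main analysis.

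**What to change.** In SAP 6.4, keep the subgroup estimates and add the following, descriptively and without p-values:

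- For each factor, the between-subgroup difference in treatment effect at Day 29 (Week 4 for Peak Pruritus NRS) with a 95% CI.
- For the MMRM endpoints, obtain it from a treatment-by-subgroup-by-visit contrast or as the difference of the independent subgroup estimates. State which.
- For the two ISGA endpoints, use the difference of risk differences. Calculate it in each imputed data set and combine as in SAP 5.3.
- For age, give each contrast against a named reference group. Ages 18 and older would serve all endpoints.
- For Peak Pruritus NRS, compare only 12–17 with 18 and older, because the scale is not collected under 12.
- Name region as country: China and Japan.
- State that the differences are imprecise (for EASI about ±14.5 points at 50:50 and ±16.8 at 25:75), that a difference interval including zero does not establish consistency, and that a subgroup interval including zero is not by itself evidence of inconsistency.

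The cost is some SAP wording and one extra column per subgroup table. The downside is that the intervals for the differences will be visibly wide. The primary endpoint and its analysis do not change, so the SAP's condition for a protocol amendment (SAP 2) is not met.

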6.5. Baseline and Other Summaries and Analyses

6.5.1. Baseline Summaries

Baseline variables will be summarized. Demographics and baseline characteristics will be summarized according to Pfizer standards.

6.5.2. Study Conduct and Participant Disposition

Subjects evaluation, disposition, discontinuation will be summarized according to Pfizer standards.

6.5.3. Study Treatment Exposure

The extent of exposure to study drug in each treatment group will be summarized by the total number of days of dosing, total number of applications, total amount of study drug applied, and number and percentage of subjects who are compliant with the dosing regimen.

During Days 1–29, a subject will be considered compliant with the dosing regimen if they receive at least 45 but no more than 67 (ie, 80%–120%, inclusive) of the expected 56 total doses to be administered between Baseline/Day 1 and Day 29, and has not missed 6 or more consecutive doses during the treatment period.

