5.3. Subject Compliance

Subject/a parent/legal guardian will apply crisaborole ointment, 2% or Vehicle to the subject at home; compliance will be captured and completed by the subject/parent/legal guardian/legally acceptable representative using a dosing diary provided by the site. The subject and parent/legal guardian (if applicable) will be instructed to complete the Dosing Diary starting with the first dose applied in the clinic on Day 1, then BID through Day 28 (ie, each time investigational product is applied) for the investigational product doses applied at home. In special situation if the subject come to the clinic in the afternoon, two doses (8-16 hours apart) or single dose could be administered on Day 1, if single dose is administered on Day 1, a morning dose will be applied at Day 29 for these special subjects in order to keep 56 doses. Subjects and parents/legal guardians (if applicable) will be instructed to bring the Dosing Diary and all dispensed investigational product supplies to the clinic at Days 8, 15, 22, and 29.

A subject will be considered compliant with the dosing regimen if the subject applies at least 80% but no more than 120% of the expected applications during the investigational product application period and has not missed 6 or more consecutive doses. This will be verified by the dosing records. Subjects having missed doses of IP will be re-educated on the importance of compliance.

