Regimen: Investigational product will be applied BID to all treatable AD involved areas (excluding the scalp) identified at Baseline/Day 1 through Day 28. The initial dose application on Baseline/Day 1 will be applied in the clinic, and all subsequent doses will be applied at home. Subjects and/or parents/legal guardians will be instructed to apply enough investigational product to cover each lesion with a layer of ointment. A total of 56 doses are expected to be applied between Baseline/Day 1 and Day 29, inclusive. In the event the scheduled Day 29 (End of Treatment) Visit does not occur on Day 29, eg, due to an unavoidable scheduling conflict, the subject and parent/legal guardian (if applicable) will be instructed to continue investigational product application BID through the evening before the day that the rescheduled End of Treatment Visit is to occur.

Investigational product will continue to be applied to all treatable AD involved areas (excluding scalp) identified at Baseline/Day 1 regardless of whether they become clinically clear prior to Day 29. Investigational product will also be applied to any new treatable AD involved areas that appear following Baseline/Day 1.

Subjects and parents/legal guardians (if applicable) will be instructed to apply evening (PM) doses approximately 8–16 hours after the morning (AM) doses (eg, if an AM dose is completed at 8:00 AM, the PM dose can be applied anytime between 4:00 PM and 12:00 AM). Caregivers or partners may also be ones to apply investigational product, especially for areas that a subject cannot reach, even in adults. The first dose is preferred to be administered in the morning on Day 1 if applicable. In special situation if the subject come to the clinic in the afternoon, two doses (8-16 hours apart) or single dose could be administered fine to only administer the PM dose on Day 1, if single dose is administered on Day 1, a morning dose will be applied at Day 29 for these special subjects.

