6.2. Time Windows for Study Procedures

Allowable time windows for visits/contacts are as follows:

- Screening visit: up to 35 Days prior to Day 1/baseline;
- Day 1 Visit: Day 1;
- Day 8 Visit: Day 8 \pm 1 day;
- Day 15 Visit: Day 15 \pm 3 day;
- Day 22 Visit: Day 22 \pm 3 day;
- Day 29 End of Treatment Visit: Day 29 \pm 3 day;
- Follow up telephone contact 1: Day 36 \pm 3 day;
- Follow up telephone contact 2: Day 60 \pm 3 day.

Refer to the [Schedule of Activities](#) for a complete list of assessments to be performed during the study.

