9. DATA ANALYSIS/STATISTICAL METHODS

Detailed methodology for summary and statistical analyses of the data collected in this study is outlined here and further detailed in a statistical analysis plan (SAP), which will be maintained by the sponsor. The SAP may modify what is outlined in the protocol where appropriate; however, any major modifications of the primary endpoint definitions or their analyses will also be reflected in a protocol amendment.

Efficacy analyses will be performed on the Full Analysis Set (FAS) which includes all subjects who are randomized and dispensed investigational product. Analyses based on the Per Protocol Analysis Set (PPAS) will be considered supportive. The PPAS includes all subjects in the FAS who complete the Day 29 evaluation without any major protocol deviations. Safety analyses will be performed on the Safety Analysis Set (SAFETY) which includes all subjects who are randomized and received at least one confirmed dose of investigational product.

Major protocol deviations will be summarized. Noncompliance with investigational product administration requirement will be summarized in terms of number of applications, number of days dosing, amount of drug used, and compliant status. A subject will be considered compliant with the dosing regimen if the subject applies at least 80% but no more than 120% of the expected applications during the investigational product application period, and has not missed 6 or more consecutive doses.

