4. ANALYSIS SETS

Population	Description
Full Analysis Set (FAS)	All subjects randomized and dispensed study drug, subjects are assigned to the randomized treatment regardless of what treatment was received.
Per Protocol Analysis Set (PPAS)	All subjects in the FAS who complete the Day 29 evaluation without any major protocol deviations.
Safety Analysis Set	All subjects who are randomized and received at least one confirmed dose of investigational product. The subject will be assigned to the randomized treatment group if he received at least one dose of the randomized treatment. The subject will be assigned to the other treatment group if he does not receive any of the randomized treatment.

Specifically, PPAS will include subjects in the FAS who meet all of the following criteria:

- Met all of the Inclusion Criteria and none of the Exclusion Criteria;
- Have not taken any prohibited concomitant medications during the treatment period;
- Completed the Day 29 Visit, including the Day 29 efficacy evaluation of EASI and ISGA, subjects ≥ 12 years who have missing Week 4 Peak Pruritus NRS evaluation will be excluded;
- Have applied 80%–120% of the total number of expected doses (56 doses) during the treatment period;
- Have not missed 6 or more consecutive doses during the treatment period;
- Were in the visit window (± 3 days) for the Day 29 Visit.

Subjects who prematurely discontinue from the study due to lack of efficacy or a treatment related TEAE will be placed back into PPAS.

Data for all participants will be assessed to determine if participants meet the criteria for inclusion in PPAS prior to unblinding and releasing the database and classifications will be documented per standard operating procedures.

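### The SAP judges every subject against 56 expected doses, although end visits on Day 26 to Day 32 are accepted and 50 to 62 doses may be scheduled, so some subjects near the 80% and 120% limits may be misclassified for the PPAS

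*SAP*

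**What the plan says.** Protocol 5.3 and 9 define a compliant subject as one who "applies at least 80% but no more than 120% of the expected applications during the investigational product application period". A second condition disqualifies anyone with a run of 6 or more missed doses. The definition gives no expected dose count.

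Protocol 5.5 does give one: "A total of 56 doses are expected to be applied between Baseline/Day 1 and Day 29, inclusive". Protocol 5.3 adds a Day 29 morning dose for subjects who receive a single dose on Day 1, "in order to keep 56 doses".

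The end visit can move. Protocol 6.2 lists "Day 29 End of Treatment Visit: Day 29" with a window of 3 days either side. When the visit is not on Day 29, Protocol 5.5 has subjects "continue investigational product application BID through the evening before the day that the rescheduled End of Treatment Visit is to occur".

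The SAP uses a fixed count in two places. In 6.5.3, which refers to Days 1–29, compliance is "at least 45 but no more than 67 (ie, 80%–120%, inclusive) of the expected 56 total doses". In section 4, a PPAS member must "Have applied 80%–120% of the total number of expected doses (56 doses) during the treatment period". The same PPAS list requires that subjects "Were in the visit window" of 3 days either side for the Day 29 visit.

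**The concern.** The PPAS list admits subjects whose end visit is up to 3 days early or late, then measures all of them against the count that applies only when the visit is on Day 29. The numerator is what was applied in the subject's treatment period, whose length varies. The denominator does not vary.

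The fixed rule is therefore stricter at the lower limit for early visits and more lenient for late ones, and the reverse holds at the upper limit. Subjects close to 80% or 120% could enter or leave the PPAS because of when the visit was booked.

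The PPAS supplies the supplementary analyses of the primary and key secondary endpoints, which are meant to show the effect in subjects who followed the regimen. The criterion should measure adherence to the doses actually scheduled.

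**Working it through.** **Inputs.** Twice-daily application (Protocol 5.5); limits of 80% and 120% (Protocol 5.3 and 9); end visit on Day 26 to Day 32 (Protocol 6.2); application up to the evening before a moved visit (Protocol 5.5). Investigational product is collected at the end visit (Protocol 6.4.3), which is consistent with application also stopping when the visit is early.

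**The plan's own figure.** For a Day 29 visit the scheduled count is 2 × 28 = 56. The limits are 0.80 × 56 = 44.8, rounded up to 45, and 1.20 × 56 = 67.2, rounded down to 67. The SAP's range reproduces exactly.

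**Other visit days.** For a visit on Day D, scheduled doses are E = 2 × (D − 1). The whole-dose range is 0.8E rounded up to 1.2E rounded down. Percentages below are of E.

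| Visit day | E | 80-120% of E | Fails 45-67 but within 80-120% of E | Passes 45-67 but outside 80-120% of E |
|---|---|---|---|---|
| 26 | 50 | 40-60 | 40-44 (80.0-88.0%) | 61-67 (122.0-134.0%) |
| 27 | 52 | 42-62 | 42-44 (80.8-84.6%) | 63-67 (121.2-128.8%) |
| 28 | 54 | 44-64 | 44 (81.5%) | 65-67 (120.4-124.1%) |
| 29 | 56 | 45-67 | none | none |
| 30 | 58 | 47-69 | 68-69 (117.2-119.0%) | 45-46 (77.6-79.3%) |
| 31 | 60 | 48-72 | 68-72 (113.3-120.0%) | 45-47 (75.0-78.3%) |
| 32 | 62 | 50-74 | 68-74 (109.7-119.4%) | 45-49 (72.6-79.0%) |

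**Fully adherent subjects.** E runs from 50 (50/56 = 89.3%) to 62 (62/56 = 110.7%). Every value lies inside 45-67, so a subject who applies exactly what was scheduled passes the dose count on any visit day in the window.

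**The consecutive-dose rule.** It does not remove the discrepancy. A Day 26 subject with 40-44 doses has missed 6-10 of 50, and a Day 32 subject with 45-49 has missed 13-17 of 62. If the misses are scattered, the rule is not triggered.

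**Counting period.** The table applies to the PPAS criterion, which counts over the treatment period. SAP 6.5.3 refers to Days 1–29. Read literally, a subject with a Day 30, 31 or 32 visit has at most 2 × 29 = 58 scheduled doses in that period. For the compliance summary, 45 is then 45/58 = 77.6% and 67 is 67/58 = 115.5%. Doses on Days 30 and 31 could count for the PPAS but not for the summary.

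**The case against.** The strongest reply is that 56 is the protocol's own number. Protocol 5.5 states it, and Protocol 5.3, the compliance section itself, arranges a Day 29 dose to preserve it. On that view the SAP simply applies the stated count, and a fixed denominator measures completion of the planned 28-day course. This stands in part. Neither document says whether the expected number changes when the visit moves, so a reader who infers that the SAP contradicts the protocol goes further than the text. But Protocol 5.5 ties 56 to Day 1 through Day 29 and then describes a different duration when the visit moves. The compliance sentence refers to the application period, not to 56. Reading 56 as the on-schedule count is the more natural reading, though not the only one.

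Three other inferences are tempting and not supported:

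- **A calculation error.** There is none; 45-67 is exact for 56.
- **A conflict between the compliance summary and the PPAS over the denominator.** Both use 56. They differ only in the wording of the counting period.
- **Exclusion of fully adherent subjects with early visits.** None fails the dose count. The subjects affected at the lower limit have missed several doses but still meet 80% of their schedule. Those at the upper limit have applied more than was scheduled.

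A per-subject denominator also has a weakness. Day 29 and early termination are the same visit in Protocol 6.4.3. If expected doses ran to any end visit, a subject who terminated on Day 11 would have 2 × 10 = 20 expected doses and could score 100%. This objection stands, and the fix has to be limited accordingly.

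**Conclusion.** The point holds as a minor one. Because the PPAS accepts visits on Day 26 to Day 32, a single denominator of 56 does not match the 50 to 62 doses scheduled. As written, it would exclude a Day 26 subject with 44 of 50 doses (88%) and keep a Day 32 subject with 45 of 62 (73%).

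Calling this misclassification assumes that expected applications means doses scheduled in the subject's own application period. The need to state the denominator and the counting period does not depend on that assumption.

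The number of subjects affected cannot be computed, because the documents give neither the distribution of doses applied nor the share of end visits away from Day 29. The same rule applies in both arms, and PPAS membership is fixed before unblinding.

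A reader might infer a threat to the primary result. The documents do not support that: the main analyses of the primary and key secondary endpoints use the full analysis set, and Protocol 9 calls PPAS analyses supportive. The effect is confined to those analyses and the exposure summary.

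**What to change.** In SAP 4 and SAP 6.5.3:

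- **Subjects who complete the end-of-treatment visit on Day 26 to Day 32.** Set expected doses to those scheduled from Day 1 to the day before the actual visit, 2 × (visit day − 1), and apply 80-120% to that number.
- **Single dose on Day 1.** Carry over the protocol's adjustment: 1 + 2 × 27 + 1 = 56 for a Day 29 visit. The protocol does not say whether the extra morning dose moves with a rescheduled visit. That wording should be clarified and the count made to follow it; the difference is one dose.
- **Early discontinuers.** Keep the planned 56, so that stopping early is not scored as full compliance.
- **Counting period.** Use the same period in both sections, in place of the treatment period in one and Days 1–29 in the other.

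If the sponsor prefers a fixed 56 for everyone, the SAP should say so and state which days count.

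The cost is one derived variable and SAP wording. It should be settled before the PPAS classification that SAP 4 places ahead of unblinding.
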